If the clinical-research team member is the first point of contact discussing research in detail, clients are given the opportunity to participate in a clinical trial, learn about the potential benefits of treatment, as well as the risks and alternatives. This process follows a core GCP principle of *respect for persons and beneficence* in that all clients are given the opportunity to choose if they want to participate in a clinical trial or not after receiving detailed information about the potential risks, benefits, and alternatives to participation. Efforts are taken to provide all possible options and alternatives to reduce any perceived or actual pressure on clients. Additionally, our consent form is structured in a way that participants can decline aspects of the study and still participate in others and receive treatment. If families choose not to participate in research, they are provided with the standard of care at the BBS and MAC, which includes assessment and treatment services as usual.

Sample Size

A Monte-Carlo simulation study with 1000 replications, moderate treatment effect ($d = 0.5$) α of 0.05 and β of 0.2, and 25% as the proportion mediated resulted in a required sample size of $N = 168$. We anticipate an attrition rate for both the intervention arm and the waitlist arm to be 20%, so we increased our sample size to 202. The Child, Youth and Family Services at CAMH and Maplewoods Centre at Guelph receive approximately 400 new child referrals per year within the age range and diagnostic criteria, so this target is quite feasible.

Clinical Records

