Videos will be recorded using an ipadaudio will be recorded via a digital recorder for the purpose of transcription, qualitative coding and fidelity checks. Recordings will be transferred via secure file transfer to the research team at the University of Guelph for transcription and coding. Once transferred, the video and audio recordings on the devices will be deleted from the recording devices and will be stored on encrypted hard drives at CAMH and secure servers at Guelph. The folder containing all video/audio recordings will be accessible only to members of the research team who have received appropriate training. Video and audio recording files will be retained at both sites for 10 years.

Once a participant agrees to participate in this study and signs the consent form, a research note will be generated on their medical record.

Participant Randomization

Stratified randomization by gender (boy, girl and non-binary) and age group (ages 8 – 10, 11 – 13, 14 – 15) will be employed to ensure balance in sample size between treatment and control groups with regard to gender and age randomization. REDCap will be employed and will allocate the participants based on a computer-generated randomization list using random block sizes. Allocation concealment will be achieved since the person making this assignment will have no awareness or control over the randomization schedule.

Data Collection

Measurement for this study will be multi-modal and will consist of questionnaires for the parent(s)/caregiver(s) and child, behavioural/cognitive tasks, a parent-child interaction task, and physiological measures. Data collection will be conducted by trained research staff with the supervision of the study investigators. The study investigators will conduct regular meetings with the

Parent and child questionnaires will be administered electronically via REDCap. In order to ensure consistency between the two sites (CAMH and Guelph), we will use a shared REDCap Project to administer questionnaires to participants. REDCap questionnaires, behavioural/cognitive tasks, parent-child interaction task, and physiological measures will be completed at each study visit. Additionally, parents and children will complete brief weekly questionnaires via secure, encrypted links from REDCap.

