Preliminary analyses will test for significant differences in demographic factors between the MATCH and waitlist groups; significant factors will be covaried in our models. In the unlikely event that medication discrepancies are discovered between the two treatment groups, we will equate the groups by imposing propensity scores-based weighting in the analysis. An exploratory factor analysis (EFA) will examine whether the emotion regulation variables load onto a broad latent construct. Variables that do not load on the same factor will be examined independently within our mediation models. Latent Growth Curve (LGC) mediation modeling, which will account for the nested structure of the data as well as potentially unequally spaced time points, will test whether improvements in emotion regulation mediate improvements in symptoms as a result of MATCH treatment. We will conduct two types of mediation analyses corresponding to our operationalization of treatment response – pre-post change and trajectory of change. First, emotion regulation (latent biobehavioural regulation factor(s) from the EFA) will be modeled as a latent change from baseline to the 3-month quarterly assessment, and symptom change (CBCL/YSR internalizing and externalizing scores) will be modeled as a latent change from baseline to the post assessment. Our predictor will be specified as MATCH vs. Waitlist to ensure we can derive conclusions about the impact of MATCH on emotion regulation and symptoms. To test the mediated effect, we will apply the recommended bootstrap-based product of coefficients, which will yield bias-corrected 95% CIs based on the recommended asymmetric CI method. Second, to understand trajectories of change during MATCH treatment, we will apply LGC modeling to examine latent slopes of change in emotion regulation (weekly CADS) and symptoms (weekly BFS) and explore the temporal relations between the two trajectories. This will allow us to understand the temporal order and bi-directionality of changes in regulation and symptoms. In both modeling approaches, we will co-vary child age, gender/sex, medication use, puberty status, ethnicity, and treatment fidelity. We will apply an intent-to-treat approach and full information maximum likelihood estimation to account for potential bias caused by missing data.

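### The primary mechanism objective rests on two or more mediator-outcome tests, each read from a 95% interval, with no confirmatory pair named, while the alpha of 0.05 and N = 168 fit a single mediated effect

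*Protocol*

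**What the plan says.** The Rationale and Study Objectives section makes the mechanism question the primary objective.

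The Sample Size section describes a Monte-Carlo simulation with a treatment effect of d = 0.5, "α of 0.05 and β of 0.2, and 25% as the proportion mediated". It arrives at 168 participants, raised to 202 for attrition. It names neither the mediator nor the outcome.

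The Data Analysis section sets the testing scheme:

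- **Mediators.** An EFA decides whether the regulation variables form one broad construct. The section allows for more than one factor, and "Variables that do not load on the same factor will be examined independently within our mediation models".
- **Outcomes.** The response side of the pre-post model is "symptom change (CBCL/YSR internalizing and externalizing scores", without a count. The YSR is completed only by children aged 11 to 15 (Symptoms section).
- **Criterion.** The mediated effect is tested by a bootstrap product of coefficients with bias-corrected 95% intervals.
- **Decision.** No mediator-outcome pair, testing order or success rule is tied to the primary objective. Nothing is said for or against a multiplicity adjustment.

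A second model, on weekly CADS and BFS slopes, is worded partly as exploration and is not counted here.

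**The concern.** One alpha and one sample size serve one mediated effect, but the analysis produces several, and how many is known only once the EFA has been run on trial data. The measurement table lists questionnaires, physiology, tasks and observational coding as regulation measures, from different reporters. More than one mediator is therefore a realistic outcome, and the protocol itself provides for it.

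Without a named pair, a reader of the results cannot tell which interval was meant to answer the primary question. If one interval among several excludes zero, it can be presented as evidence of mechanism, although the chance of that happening without any mediation may be well above 5%. An adjustment added later would not fully cure this. The sample size was set for a single test, so sharing alpha over several pairs would cost power that the protocol has not budgeted for.

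**Working it through.** **Inputs from the protocol.** Alpha 0.05, power 0.80, d = 0.5, 25% mediated, N = 168 (Sample Size); a 95% interval per mediated effect (Data Analysis). The indirect effect is ab = 0.25 × 0.5 = 0.125.

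**Assumptions, not stated in the protocol.** Two-sided tests; 1:1 allocation, read from the aim "to ensure balance in sample size between treatment and control groups"; unit residual variances; path split a = 0.5 (treatment to mediator), b = 0.25 (mediator to outcome), direct effect 0.375. The joint-significance test, which requires both paths to be significant, stands in for the asymmetric interval.

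**Step 1: reproduce N = 168.** With 1:1 allocation, a has standard error 2/√N, so its expected z is 0.5√N/2 = 0.25√N. For b the expected z is also 0.25√N. Joint power of 0.80 needs √0.80 = 0.894 on each path, which is z = 1.25. Hence

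N = ((z_alpha + 1.25)/0.25)² = ((1.96 + 1.25)/0.25)² = 165.

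Simulation at N = 168 (4,000 replications per run) gave power of 0.795 to 0.803. The stated figure therefore fits one mediator and one outcome at two-sided 0.05. It depends on the split: holding ab = 0.125 and varying a from 0.3 to 0.8 gave power between 0.49 and 0.80.

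**Step 2: count the tests.** One factor against internalizing and externalizing gives 2 tests. One factor with CBCL and YSR modelled separately gives 2 × 2 = 4. Each further mediator adds 2 or 4, so three mediators give 6 or 12.

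**Step 3: chance of at least one false mediation finding.** For k independent tests at a true 5% each, the rate is 1 − 0.95^k: 9.75% (k = 2), 18.5% (4), 33.7% (8), 46.0% (12).

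Simulated at N = 168 (3,000 replications, joint significance, correlations of 0 to 0.5 among mediators and among outcomes):

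| Mediators × outcomes | Treatment moves mediator (a = 0.5), b = 0 | Neither path real (a = b = 0) |
|---|---|---|
| 1 × 2 | 7-9% | 0.3-0.5% |
| 1 × 4 | 14-18% | 0.8-0.9% |
| 2 × 4 | 24-31% | 1.6-1.9% |
| 3 × 4 | 34-43% | 2.5-2.8% |
| 7 × 4 | 55-73% | 6.0-7.6% |

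**Step 4: sensitivity to the planned interval.** A simulation of the bias-corrected bootstrap itself at N = 168 with b = 0 gave a per-test error of 8.1% at a = 0.5 and 4.8% at a = 0.3. Two independent tests would then give 1 − 0.919² = 15.5% and 1 − 0.952² = 9.4%; four would give 28.7% and 17.9%. The middle column above is therefore not an overstatement at a = 0.5.

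**Step 5: what sharing alpha would cost.** Putting the Bonferroni level 0.05/k into the formula of Step 1, N for 80% power is ((2.498 + 1.25)/0.25)² = 225 for four tests and ((2.734 + 1.25)/0.25)² = 254 for eight, before attrition. At N = 168 the simulated power of one test falls from about 0.80 to about 0.58 (four tests) and 0.47 (eight).

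**The case against.** The strongest reply is that much of this is silence, and that the statistical analysis plan, not shown here, may name a primary pair and an adjustment. That is a fair limit. A reader might infer that the protocol commits to unadjusted testing, or that any one significant interval wins. It says neither. It fixes a 95% level, which is the unadjusted one, and leaves open which result decides. The error rates above apply only if any one interval is read as sufficient.

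A reader might also infer a minimum of four tests. The text gives no count: the slash between CBCL and YSR could mean combined informants, so the supportable minimum is two. The EFA may also return a single factor, which is the case the trial hopes for.

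Nor does the protocol promise a family-wise error of 0.05. That figure is an input to the power simulation, and each test does run at a nominal 0.05, so this is not a self-contradiction.

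Finally, the inflation depends on the null. If treatment moves no mediator and no mediator drives symptoms, mediation tests are very conservative, and the overall rate stays below 5% unless mediators are many. This is correct, but it is the less relevant case, because the trial expects treatment to improve regulation. What then needs protecting against error is the second link, from regulation to symptoms.

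What survives is what the protocol does state: several mediators and outcomes, a 95% interval for each mediated effect, and an alpha and N that suit one.

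**Conclusion.** The point holds in a limited form. The plan applies a 95% interval to two or more mediator-outcome tests under its primary objective and names no confirmatory pair, although its alpha and N = 168 correspond to a single mediated effect.

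The size runs from modest (7-9%, one mediator and two outcomes) through 14-18% (one and four) to serious (34-43%, three and four). These figures assume that treatment moves the mediator with a = 0.5, that the mediator has no effect on symptoms, that correlations lie between 0 and 0.5, and that one interval excluding zero would be taken as support. The match to N = 168 rests on an assumed path split.

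The change should be made because the primary claim depends on it and it is cheap, but the protocol is not shown to guarantee a false-positive rate of any particular size.

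**What to change.** Before outcome data are analysed, state in the Data Analysis section:

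1. One confirmatory test of the primary objective: the effect of MATCH versus waitlist through the broad regulation factor on one pre-named CBCL score. A CBCL score is the natural choice because it is collected at all ages, whereas the YSR is not.
2. If the EFA yields more than one mediator, Holm across those mediators for that one outcome.
3. All other mediator-outcome pairs are supportive and cannot establish the primary claim on their own.

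The Sample Size section should name the same pair.

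**Cost.** With one mediator this is wording only, and alpha and N = 168 stand. With several mediators the thresholds tighten and each test loses some power. Under the assumptions of Step 1, the expected z per path at N = 168 is 0.25√168 = 3.24. At the strictest Holm step, power is Φ(3.24 − 2.241)² = 0.71 for two mediators and Φ(3.24 − 2.394)² = 0.64 for three, against Φ(3.24 − 1.96)² = 0.81 for one. That loss is smaller than if alpha were shared over every mediator-outcome pair.

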Following the intervention or waitlist period, our team will conduct post- assessments. The post-assessments will allow us to analyze any changes in biobehavioural regulation and compare the differences between the intervention and control arms. Participants in the control arm will complete the post assessment approximately 4-6 months after their initial assessment, or prior to them being picked up off the waitlist for treatment in the clinic. . As screening and enrolment are ongoing, we will consistently clean data and engage in quality assurance procedures to ensure our methods are rigorous and meet scientific standards.

Participant Recruitment

Children will be recruited from the Child, Youth, and Emerging Adult Program (CYEAP) at CAMH and at the Maplewoods Centre for Family Therapy and Child Psychology at the University of Guelph.

Approximately 250 families (children aged 8 – 15, and their parent(s)/caregiver(s)), seeking psychotherapy for child anxiety, depression or disruptive behaviour will be recruited for this study. Families recruited from CAMH will have been referred to the Better Behaviours Service or Mood & Anxiety Clinic, or will be on the psychiatric assessment waitlist. Many families on the waitlist wait over a year for psychiatric evaluation, and many do not need or benefit from an assessment because they have been referred specifically for psychosocial treatment, and may already have a diagnosis and prescribed medication. To reduce the wait times for families and reduce the assessment burden, clinicians will screen families before their psychiatric assessment to identify children who may benefit from directly receiving psychosocial treatment without needing a psychiatric assessment first. These families will be contacted and asked to complete a short clinical screening (i.e. reason for referral) and approached to participate in research if the clinical team thinks the family would be a good fit. This process follows a similar procedure previously approved for use in our clinic (REB #018/2022).

Initial Research Contact

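### The bias-corrected bootstrap interval chosen to test mediation exceeds the stated alpha of 0.05 (about 7–8% in a simplified model) when one path is zero and the other is moderate

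*Protocol*

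**What the plan says.** The Data Analysis section tests whether gains in emotion regulation mediate the effect of treatment on symptoms. The exposure is the randomised arm ("Our predictor will be specified as MATCH vs. Waitlist"), the mediator is change in regulation up to the 3-month visit, and the outcome is symptom change up to the post-treatment visit. For the mediated effect it states: "we will apply the recommended bootstrap-based product of coefficients, which will yield bias-corrected 95% CIs based on the recommended asymmetric CI method".

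The Sample Size section describes "A Monte-Carlo simulation study with 1000 replications, moderate treatment effect" (d = 0.5), with "α of 0.05 and β of 0.2" and "25% as the proportion mediated", and arrives at N = 168. It then allows for attrition: "attrition rate for both the intervention arm and the waitlist arm to be 20%, so we increased our sample size to 202".

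The protocol does not give the two component paths, does not say whether d = 0.5 is the total effect or the path to the mediator, and does not say which mediation test the power simulation used.

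**The concern.** Mediation requires two non-zero paths: a, from treatment to regulation, and b, from regulation to symptoms given treatment. No mediation therefore covers many situations, and a test must hold its level in each plausible one. Two matter here: treatment improves regulation but regulation does not drive symptoms (b = 0), or regulation is related to symptoms but treatment does not move it (a = 0).

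When the two estimates are both well away from zero, the bootstrap distribution of their product is skewed away from zero. More than half of the resamples then fall on the zero side of the estimate. The bias correction responds by moving both limits away from zero, so the interval excludes zero more often than it should.

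At stake is the primary objective, regulation as a mechanism of change. In those situations mediation would be declared more often than the stated alpha allows. The protocol itself fixes the interval type, so this is not a detail left to a later analysis plan.

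**Working it through.** **Inputs from the protocol.** Alpha 0.05, taken as two-sided to match a 95% interval; power 80%; d = 0.5; proportion mediated 25%; N = 168, enrolment 202; attrition 20%.

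**Assumptions.** 1:1 allocation (84 per arm); d = 0.5 read as the total effect; one observed mediator; residual SDs of 1; no covariates in the main runs. Then a × b = 0.25 × 0.5 = 0.125 and the direct effect is 0.5 − 0.125 = 0.375. The split a = 0.5, b = 0.25 is one that gives 0.125.

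**Reproducing N = 168.** Joint-significance power is approximately the product of two powers:

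- path a: Φ(0.5 × √(84/2) − 1.96) = Φ(1.28) = 0.90
- path b: Φ(0.25 × √168 − 1.96) = Φ(1.28) = 0.90
- product: 0.90 × 0.90 = 0.81

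Simulation gives 79.5% for joint significance and 78.5% for the percentile bootstrap. So N = 168 is recovered, within 2 points of 80%, under these assumed paths.

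**The two intervals.** Both use the same resamples. The percentile limits are the 2.5% and 97.5% quantiles. For the bias-corrected interval, z0 = Φ⁻¹(share of resamples below the estimate), and the limits are the quantiles at Φ(2·z0 − 1.96) and Φ(2·z0 + 1.96).

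**Rejection rate when the true mediated effect is zero.** 1000 resamples and 8000 simulated trials per row; the Monte Carlo standard error is about √(0.075 × 0.925 / 8000) = 0.3 points.

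| N | a | b | Bias-corrected | Percentile | Joint significance |
|---|---|---|---|---|---|
| 168 | 0 | 0 | 0.7% | 0.2% | 0.3% |
| 168 | 0 | 0.14 | 3.8% | 1.6% | 2.0% |
| 168 | 0 | 0.25 | 7.5% | 4.1% | 4.3% |
| 168 | 0 | 0.39 | 6.9% | 5.0% | 4.7% |
| 168 | 0 | 0.59 | 6.2% | 5.5% | 4.9% |
| 168 | 0.2 | 0 | 2.6% | 1.0% | 1.2% |
| 168 | 0.5 | 0 | 8.2% | 4.8% | 4.7% |
| 168 | 0.8 | 0 | 7.2% | 5.3% | 4.9% |
| 202 | 0 | 0.25 | 8.3% | 5.1% | 5.1% |
| 202 | 0 | 0.39 | 7.1% | 5.2% | 4.7% |
| 202 | 0 | 0.59 | 5.6% | 5.1% | 4.8% |
| 202 | 0.5 | 0 | 7.6% | 4.8% | 4.7% |

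**Stability.** With 5000 resamples the rate at a = 0, b = 0.25 is 7.6%, so too few resamples is not the cause. Two further simulations of the moderate one-zero-path cases at N = 168 gave 6.8–7.6% and 7.1–8.1%, against 4.3–5.4% and 4.3–5.1% for the percentile interval. At a = 0.5, b = 0 the estimates range from 6.8% to 8.2%, so about 7–8% is as precise as the figure should be. Adding eight covariates (2000 trials per case, standard error about 0.6 points) gave 7.5–8.3% against 3.3–4.8%.

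**Coverage at the planning alternative** (a = 0.5, b = 0.25, N = 168). The bias-corrected interval misses the true value 4.4% of the time, so coverage is about 95.6%.

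**Power at N = 168.** At a = 0.5, b = 0.25 it is 84.8% (bias-corrected) and 78.5% (percentile), a loss of 6.3 points. Four other splits of a × b = 0.125 gave 70–83% against 64–76%, a loss of about 6 to 7 points each. With the eight covariates, power at a = 0.5, b = 0.25 was 83% against 75%.

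**Completers.** 202 × 0.80 = 161.6, about 162. The approximation above then gives Φ(0.5 × √(81/2) − 1.96) × Φ(0.25 × √162 − 1.96) = 0.89 × 0.89 = 0.79, about two points below the 0.81 at 168.

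**The case against.** The strongest reply has four parts.

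- **The rate depends on the null.** It runs from 0.7% to 8.3%, and in several no-mediation situations the test is conservative. This stands, and the point is limited accordingly. It does not remove the problem: a test's level is judged at its least favourable plausible null, and a treatment path near 0.5 with b = 0 is plausible in a trial planned on d = 0.5.
- **The figures rest on assumptions.** The protocol gives neither a nor b, and the planned model has latent change scores, factors from an exploratory analysis, covariates, nesting and full-information likelihood for missing data. This stands: the direction is well supported, the exact rate under the planned model is not known.
- **The methods trade power against type I error, and this one was openly pre-specified.** That is true, but the extra 6 points of power come with exceeding the alpha the protocol states, so they are not available at that alpha.
- **The excess of 2 to 3 points is small** beside the number of mediators and symptom scores that may be tested. That bears on priority, not on whether the level is met.

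Stronger readings are tempting. A reader might infer a single false-positive rate of 7 to 7.5% whenever there is no mediation, and hence 40 to 50% more false claims than planned (7/5 = 1.4; 7.5/5 = 1.5); the table rules out any one such rate. A reader might infer that the interval fails as a 95% interval in general; coverage at the planning alternative is about 95.6%. A reader might also infer that N = 168 was derived for the bias-corrected test, or that the change leaves power fully at 80%. The protocol does not name the test behind N = 168, and the simulated percentile power is about 79% at best among the splits tried.

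**Conclusion.** The point holds in limited form. With one path zero and the other moderate, at N = 168, the specified interval rejects about 7–8% of the time against a stated 5%, while the percentile interval from the same resamples stays at about 4–5%. The excess persists at N = 202 (7.1–8.3% in the moderate cases) and shrinks when b is large (5.6–6.2% at b = 0.59). The rate is below 5% when both paths are zero or the non-zero path is weak.

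This rests on an observed-variable, single-mediator model with unit residual SDs, 1:1 allocation and assumed paths. It is a modest departure from the stated level in the main mediation test, and worth correcting before analysis because the correction is cheap.

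**What to change.** In the Data Analysis section, specify a percentile bootstrap 95% interval for the product of coefficients as the test of mediation, and report the bias-corrected interval as a sensitivity result only. A Monte Carlo or distribution-of-product interval is an alternative; neither was simulated here. All of these remain asymmetric, so the protocol's stated preference is kept.

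The change is one phrase and one software option, with no extra data or resampling. The real cost is power: at a = 0.5, b = 0.25 and N = 168 it falls from about 85% to about 79%, roughly the planned 80%. It may be a few points lower with covariates (75% in the eight-covariate check) or with about 162 completers. The Sample Size section should therefore state the assumed a and b and the mediation test used, and the power simulation should be rerun with the chosen interval to confirm that the enrolment target is still adequate.

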Study Design

This project will have several components, which we anticipate will unfold over the course of 5 years. The first step of the process will be training research and clinical staff; practicum students, psychology residents, and staff clinicians at CAMH on administering the Modular Approach to Therapy for Children with Anxiety, Depression, Trauma, and Conduct Problems (MATCH-ADTC) treatment. The study investigators will be primarily involved in training clinical staff on MATCH-ADTC treatment. They will not be directly involved in administering care, but they will be responsible for supervising practicum students and residents administering care. These students are clinical trainees in a doctoral program for clinical psychology, supervised by registered psychologists at CAMH (e.g., [name], [name]). These students have previously completed coursework and training in therapeutic methods. When matching clients to students, we will consider the expected length of treatment in relation to the length of their practicum or residency. Most practicums and residencies range from 9 months to 12 months, which will provide ample time to complete most courses of treatment. In the case that a student is unable to complete a course of treatment for a client, we will ensure continuity of care as is standard within our clinical services. There would be a plan for a warm transfer, where another trainee or clinician would continue treatment.

Children and their parent(s)/caregiver(s) will be recruited on an ongoing basis from two outpatient children's mental health clinics (CAMH and University of Guelph). Senior research staff will screen families, enroll them in the study, and conduct pre-treatment assessments. After enrolment and collection of initial measures, participants will be randomly assigned to the intervention arm or the waitlist control arm. We anticipate that the duration of both MATCH-ADTC treatment and the waitlist will range between 4 – 6 months, which is similar to the usual wait times for services at both clinics.

During this period, participants in both arms will complete brief weekly measures, which consist of very brief symptom scales. Participants will be required to complete quarterly assessments (approximately 3 months following their initial assessment), which will consist of symptom scales, medication tracking, clinical interviews, experimental tasks and physiological measures.

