Previous studies involving randomized waitlist controlled studies have established that MATCH-ADTC treatment is more effective than usual care. The justification of the control arm in this study is to allow us to evaluate the changes in biobehavioural regulation as a consequence of MATCH-ADTC treatment. The waitlist control exists to support our hypothesis that changes in emotion regulation are not merely due to the passage of time or normal emotional/psychological development in children.

The control arm of this project will consist of a no-treatment, waitlisted group. Participants in the waitlist condition will remain on the waitlist for standard usual care, and the estimated wait time is approximately 4-9 months. While in the waitlist control arm, participants are required to complete 75% of the weekly measures and attend both the quarterly (3-month) and the post-test study visit. If participants decide not to continue with the study, or they are lost to follow-up, they will be considered a drop-out in the Big Feelings Study, but their referral will remain open for usual care and they will remain on the clinic waitlist. Upon completion of the post-assessment, participants in the waitlist condition will be offered a bridging treatment (usually MATCH-ADTC treatment) until their usual care standard treatment spot becomes available, at which point they can decide whether they would like to continue with the bridging treatment or move to the standard care. Therefore, participants assigned to the control arm will also receive high quality, evidence-based treatment.

Compensation

Children and their parent(s)/caregiver(s) will be compensated for their participation. They will be provided with gift cards at each study visit and for completion of the weekly surveys. If participants are only able to complete the questionnaires, they still receive a portion of honorarium (see table, where the amount for “questionnaires” indicate how much participants can receive as honorarium for partial completion).

	Pre-Test Visit	Weekly Surveys	Quarterly Visit(s)	Post-Test Visit	
Parent	\$30 questionnaires only \$40 both questionnaires and in person visits	\$2 per survey \$5 bonus for every 5 completed	\$30 questionnaires only \$40 both questionnaires and in person visits	\$30 questionnaires only \$60 both questionnaires and in person visits	

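### The weekly CADS/BFS slope model is labelled mediation but, as described, names no arm predictor and no indirect effect, so it cannot attribute the link between the slopes to MATCH

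*Protocol*

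**What the plan says.** The Data Analysis section of the protocol opens its account of the latent growth curve models by saying that they "will test whether improvements in emotion regulation mediate improvements in symptoms as a result of MATCH treatment". It continues: "We will conduct two types of mediation analyses corresponding to our operationalization of treatment response", these being pre-post change and trajectory of change.

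The pre-post model is fully framed. It has a latent change in regulation to 3 months, a latent change in symptoms to the post assessment, and a bootstrapped product of coefficients. Its exposure is explicit: "Our predictor will be specified as MATCH vs. Waitlist to ensure we can derive conclusions about the impact of MATCH".

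The trajectory model follows: "Second, to understand trajectories of change during MATCH treatment, we will apply LGC modeling to examine latent slopes of change in emotion regulation". It uses weekly CADS for regulation and weekly BFS for symptoms, and its task is to "explore the temporal relations between the two trajectories". No arm predictor, arm contrast or indirect effect is given for it.

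Three other places bear on this:
- Study Design says that "participants in both arms will complete brief weekly measures".
- Control Group says that the waitlist is there to support the hypothesis that "changes in emotion regulation are not merely due to the passage of time or normal emotional/psychological development in children".
- Rationale and Study Objectives counts the rate of symptom change among the Aim 1 definitions of treatment response, and states the main hypothesis as a comparison with waitlisted controls.

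**The concern.** Mediation of a treatment effect needs treatment as the exposure. If a child's negative emotionality and problem scores fall together over the weeks, that shows the two are coupled. It does not show that MATCH moved either of them, and finding that one tends to move before the other does not change this.

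Coupling without treatment is plausible here. CADS negative emotionality and the BFS are both completed weekly by parents and children (CADS child report from age 9). Natural recovery, regression to the mean and the rater's own mood can all shift both scores together in untreated children.

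At stake is the half of the Aim 1 mechanism question that concerns rate of change. Run as described and reported under its present label, the analysis could present shared change over time as a mechanism of MATCH, although the trial collects the control data needed to tell the two apart.

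**Working it through.** The protocol gives no figure for this model, so there is nothing to reproduce. The check has two parts.

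**1. The two models side by side (Data Analysis)**

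| Element | Pre-post model | Weekly trajectory model |
|---|---|---|
| Called mediation | yes | yes |
| Mediator | latent regulation change, baseline to 3 months | CADS slope |
| Outcome | CBCL/YSR change, baseline to post | BFS slope |
| Arm as predictor | stated | not stated |
| Indirect effect | bootstrap product of coefficients | not stated |
| Covariates | stated for both models | stated for both models |

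The covariates are expressly extended to both approaches. The predictor is not; it appears only in the account of the pre-post model.

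**2. How often slopes would be associated with no effect of MATCH on regulation**

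Inputs:
- N = 168 (Sample Size section). Allocation is assumed 1:1, because no ratio is given, so 168/2 = 84 per arm.
- Two-sided 5% level, assumed.
- Correlation r between the CADS and BFS slopes, the same in all children and owing nothing to MATCH. The documents give none; the assumed range is 0.2 to 0.5.
- Slopes are treated as observed without measurement error.

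*MATCH-only association, n = 84.* By Fisher's transformation, power ≈ Φ(atanh(r)·√(n − 3) − 1.96), with √81 = 9:
- r = 0.2: 0.2027 × 9 = 1.82, and Φ(−0.14) ≈ 45%
- r = 0.3: 0.3095 × 9 = 2.79, and Φ(0.83) ≈ 80%
- r = 0.4: 0.4236 × 9 = 3.81, and Φ(1.85) ≈ 97%
- r = 0.5: 0.5493 × 9 = 4.94, and Φ(2.98) > 99%

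Simulation with 4,000 replications agrees: 45%, 80%, 97% and over 99%.

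*Two-arm test, N = 168.* Arm has no effect on the CADS slope. Mediation is declared only if both the arm-to-CADS-slope path and the CADS-slope-to-BFS-slope path (adjusted for arm) are significant. Simulated rates are about 4%, 5%, 5% and 5% for the same four correlations.

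*Limit of the two-arm test.* Now let MATCH shift both slopes by an assumed d = 0.5, with no causal path from CADS slope to BFS slope and only correlated residuals. The same test declares mediation in about 66% (r = 0.2), 89% (r = 0.3) and 90% (r = 0.5) of trials. Adding arm protects against mistaking passage of time for an effect of MATCH on regulation. It does not remove confounding between two scores given by the same rater.

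**The case against.** A reader might infer that the waitlist arm is left out of the weekly model and its data go unused. The protocol does not say so. The reference to change during MATCH states a purpose and does not define an analysis set. Weekly measures are collected in both arms, waitlist children must complete 75% of them, the lead sentence covers all the growth-curve mediation models, and "We will apply an intent-to-treat approach and full information maximum likelihood estimation" carries no restriction. Treatment fidelity as a covariate does not settle the matter either way, since it is also listed for the pre-post model, which compares both arms. This part of the objection stands: exclusion is an inference.

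The stated task is also partly exploratory, concerned with temporal order and direction, and the protocol attaches no significance rule to it. The formal randomised mechanism test is the pre-post model. This stands too, and limits the severity. It does not justify the label: if only association is meant, the analysis is not mediation.

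The 45% to over 99% range could be misread as a false-positive rate. It is the power to detect a correlation assumed to exist, using a simple test that the protocol does not plan, so finding that correlation would be a correct result about association. Only attributing it to MATCH would be wrong.

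Finally, much model detail may properly sit in a statistical analysis plan that is not shown. But the protocol itself chose the label and tied the exposure to one of the two models. A general intent-to-treat statement does not supply a predictor.

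**Conclusion.** The point holds as a mismatch between label and specification. The weekly model is called mediation and tied to an Aim 1 definition of response, but it is described only for change during MATCH, with no arm predictor and no indirect effect. Followed as written, it can show that regulation and symptoms move together; it cannot show that MATCH is why.

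On size, under assumed slope correlations of 0.2 to 0.5, 84 MATCH children and no measurement error, a significant MATCH-only association would appear in about 45% to over 99% of trials even if MATCH did nothing to regulation. The argument does not depend on a particular value: any non-zero natural correlation produces the same ambiguity.

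The correction should be made, but it is not critical. The pre-post model already carries the randomised contrast, and the remedy uses planned data.

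**What to change.** In Data Analysis, specify the weekly model as follows:
- Fit it in both arms, with MATCH versus waitlist predicting the CADS slope and the BFS slope.
- Use the word mediation only for the path from arm through CADS slope to BFS slope.
- Report the slope-to-slope relation separately by arm, for example in a two-group model.
- Describe any result from MATCH children alone as association during treatment.
- Start the clock at randomisation in both arms. Acknowledge that this includes untreated weeks in the MATCH arm, since the Consent and Assent section says that these children also wait before starting. A sensitivity analysis from treatment start would address this.

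No new data are needed; the cost is protocol wording and a somewhat larger model. There are three downsides. The estimated mechanism effect may be smaller than a within-arm correlation suggests. Waiting weeks may dilute the MATCH slope and blunt the question of temporal order. The path from CADS slope to BFS slope also stays open to same-rater confounding with arm in the model, and the protocol should say so.
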